Background and Rationale	
Each year, approximately 1500 breast biopsies (1000 microbiopsies and 500 macrobiopsies) are performed in the radiologic department of the Montpellier Cancer Institute (ICM). This exam, which is relatively easy for the radiologist, can however lead to major anxiety for patients. Indeed, previous studies show that about 50% of women undergoing a breast biopsy have significant anxiety affects. Anxiety associated with the risks of biopsy, potential breast cancer diagnosis and/or lack of routine sedation procedures increase patient concerns. Distress prior to biopsy is associated with greater pain and discomfort during the procedure. The psychological distress that persists after the biopsy is related to a worse psychological management of side effects of the biopsy breast (e.g., sensitivity, skin irritation).
 
Limiting apprehension, worry and anxiety induced by the uncertainty linked to the biopsy results and the biopsy-related pain should be an integral part of the medical care through the patient follow-up during, after and until the diagnosis is announced. In light of these challenges, new alternative methods are emerging to enhance patient knowledge, develop procedural skills, improve confidence and mitigate procedural anxiety. However, to our knowledge, few methods have been developed during this period of 'waiting-time'. Currently, only care instructions and a consultation to announce the results (about 10 days after the procedure) are proposed to patients at the end of biopsy. Patients are also encouraged to call if they suspect complications such as infection or bleeding.
 
In this context, we propose to integrate a pain management after biopsy via e-health system through the patient's medical care. Radiologist/patient communication could have an impact on patients' anxiety and health-related issues, given the challenging nature of discussions around need for breast biopsy and potential implications of the results. Indeed, paying attention and focusing on symptoms as patients experience them improves their empowerment and their adjustment to the disease.
 
Web-based systems that can provide electronic-Patient reported Outcomes (e-PRO) have been shown to prompt clinicians to intensify symptom management, to improve symptom control and to enhance patient-clinician communication patient satisfaction, as well as well-being. In addition, it is known that improved communication between patients and medical staff to less anxiety after a biopsy and that anxiety is related to pain.
 
Taken as a whole, these elements encourage the integration of e-health and e-PRO for the management of pain and anxiety in patients undergoing a biopsy. The benefits of e-PRO are still being discussed in terms of quality of life (Qol) and psychological distress. We thus propose to integrate two types of e-health intervention: 1/e-PRO collected by connected objects (smartphone or tablet) as they were used in previous studies, and 2/ e-PRO collected by a phone consultation, which values human communication between the medical staff and the patient.
 
In case of significant pain, the collection of e-PRO by any of these e-health interventions will generate an alert and a reactive and responsive care.
 
In fine, the purpose of this research is to improve the medical organization and care of post-biopsy patients by proposing an innovative connected patient technology, regardless of their remoteness from the hospital.
 
Social inequalities will be reduced by lending a tablet to patients who do not have such a device with a 4G key.

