---------------------------	---

	
 - To reduce social and territorial inequalities. - To assess satisfaction with specific study management. - To assess compliance.
Study endpoints	
Primary endpoint: Pain score assessed (by phone) via a numeric pain scale completed 4 days after biopsy (D4).
 
Secondary endpoints :
 
 - Pain score assessed using a numeric pain scale administered after to biopsy and during the consultation of results announcement (approximately D10). - Anxiety score assessed using a numeric anxiety scale administered after to biopsy, at 4 days (D4) and during the consultation of results announcement (approximately D10). - Esthetic impact score assessed using a numeric esthetic scale administered after to biopsy, at 4 days (D4) and during the consultation of results announcement (approximately D10). - Insomnia score assessed using the Index of Severity of Insomnia administered during the baseline visit and the consultation of results announcement (approximately D10). - Number of alerts that generated a phone call or number of phone calls generated directly by the patient and patient care accordingly. - Quantity, nature and dose of analgesics, anxiolytics, anti-depressants, anti-inflammatory and hypnotics used for the biopsy and its aftermath. - Adverse event in particular bleeding and infection due to biopsy recorded at 4 days (D4) and during the consultation of results announcement (about D10) by NCI-CTCAE 5.0 - Geographical distance from the reference center. - Number of tablets/4G keys made available to patients who do not benefit from them at home. - Number of positive responses to satisfaction questions related to the number of solicitations for the study and how interventions are communicated - Rate of completion questionnaire and numeric scale.

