Benefit	
Focusing on symptoms as patients experience them improves their empowerment and their adjustment to the disease.
 
e-PRO prompt clinicians to intensify symptom management, to improve symptom control and to enhance patient-clinician communication patient satisfaction, as well as well-being. In addition, it is known that improved communication between patients and medical staff to less anxiety after a biopsy and that anxiety is related to pain.
 
Taken as a whole, all these elements encourage to integrate e-health and e-PRO in the management of pain and anxiety in patients undergoing a biopsy.
 
In case of significant pain, the gathered e-PRO will generate an alert and a reactive and responsive care. In fine, this research aims to improve the medical organization and management of post-biopsy patients by proposing an innovative connected patient technology, regardless of their remoteness from the hospital.

Eligibility criteria	
1) Inclusion criteria
 
 - Patient with diagnostic breast biopsy at ICM - Age > 18 years - Informed patient and signed informed consent received - Affiliation to a social security system 
2) Non inclusion criteria
 
 - Patient without phone number - Patient with previous biopsy in 6 months prior to study - Pregnant and breastfeeding woman - Patient whose regular follow-up is initially impossible for psychological, family, social or geographical reasons - Patient under legal protection (guardianship, curatorship or safeguarding of justice)
Enrolment Procedure	
After the patient has given her informed consent to participate in the study, and after verification of all inclusion/ non-inclusion criteria, the investigator will proceed to the patient registration via a dedicated form to be sent to the Biometrics Unit of the center.

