Treatment modalities	
After breast biopsy and randomization (random bloc method and ratio 1:1:1), patients will either be in the:
 
 - Experimental Group 1: PRO gathered via a phone consultation - Experimental Group 2: e-PRO self-completed via connected objects (tablet/phone) - Group 3: Control group without e-PROs (standard care)  
Experimental Group 1 with phone consultation (n=64)
 
Experimental Group 2 with application on connected objects (phone/tablet) (n=64)
 
Group 3 without intervention (n=64)
 
D0 Biopsy R (1:1:1) N= 192
 
D4
 
D10
 
D0 = Randomization + Evaluations of pain, anxiety and esthetical impact (with numeric scale) D4 = Evaluations by phone consultation of pain, anxiety and esthetical impact (with numeric scale) D10 = Evaluations of pain, anxiety and esthetical impact (with numeric scale) during the consultation of results announcement
 
Evaluations of pain, anxiety and esthetical impact (with numeric scale) by phone consultation
 
Evaluations of pain, anxiety and esthetical impact (with numeric scale) via the application on connected objects (phone/tablet)

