Statistical considerations	
Sample size.
 
A pilot study has been performed in the radiology department including 25 patients in order to determine the pain level on average: mean = 5 and standard deviation = 3.
 
Assuming a mean pain score on day 4 equals to 5 points with a standard deviation equals to 3 in the control group, with α (two-sided) = 2.5%, power= 90%, it is necessary to include 58 patients per group (174 patients in total), to detect a difference of 2 points (according algology criteria and good practice recommendations) between control arm and each experimental arm. Finally, 192 patients will be included considering 10% non-evaluable patients.
 
Statistical analyses.
 
A statistical analysis plan (SAP) will be written before the closed database. All statistical analyses will be performed on ITT population and on PP (per-protocole) population for primary endpoint. All collected data will be described.
 
Descriptive analyses will be performed using frequency (N) and percentage (%) for categorical variables, mean / standard deviation or median / range for continuous parameters.

	
The Pearson's chi-square or the Fisher's exact test will be performed for categorical variables and the Student test or Wilcoxon / Kruskal-Wallis test for continuous parameters.
 
The primary endpoint, pain score assessed by phone 4 days after biopsy, will be compared between control and experimental arms (telemedicine vs control and smartphone vs control).
 
The secondary endpoints will be compared between control and experimental arms (telemedicine vs control and smartphone vs control) and between the two e-PRO interventions (telemedicine vs smartphone).
 
All statistical analyses will be performed with the Stata software v16.0 and a statistical report will be provided according to the current model.

Study period	
Starting date of inclusion: February 2021 Duration of inclusion: 34 months Duration of participation: 10 days (+/- 2 days) Date of end of patient follow-up: December 2023

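### Biopsy type (micro or macro) is known at allocation but not used: adjusting the D4 pain comparison for it would be a cheap, optional gain in precision, if the two types differ in pain

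*Combined protocol and SAP*

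**What the plan says.** All references are to the synopsis, which is the text available.

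- **Background and Rationale:** each year "approximately 1500 breast biopsies (1000 microbiopsies and 500 macrobiopsies) are performed in the radiologic department".
- **Eligibility criteria:** the entry condition on the procedure is "Patient with diagnostic breast biopsy at ICM", with no restriction by type.
- **Treatment modalities:** the allocation is described as "random bloc method and ratio 1:1:1". The sentence opens "After breast biopsy and randomization", and the design scheme puts the biopsy before the randomisation at D0. No stratification factor appears in the text or the scheme.
- **Study endpoints:** the primary endpoint is a numeric pain score taken by phone at D4. Esthetic impact, bleeding and infection are among the secondary endpoints.
- **Statistical considerations:** the listed tests are Pearson chi-square, Fisher, Student and Wilcoxon/Kruskal-Wallis. No covariate or stratified model is named. The sample size rests on this sentence: "Assuming a mean pain score on day 4 equals to 5 points with a standard deviation equals to 3 in the control group". A SAP is to be written before the database is closed.

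After the background section, biopsy type is not mentioned as a stratification factor, covariate or subgroup.

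**The concern.** The endpoints are consequences of the biopsy, so the kind of biopsy is a natural candidate to predict them. It is fixed before allocation and costs nothing to learn. Blocks that ignore it balance the number of patients per arm but leave the micro/macro mix to chance. Both primary comparisons use the same control arm, so an unusual mix there would move both results in the same direction.

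What is at stake is precision. If D4 pain differs by biopsy type, an unadjusted test leaves that part of the variation in the error term, where a prespecified adjustment would remove it.

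**Working it through.** **Inputs from the synopsis.** Control mean 5 and SD 3; target difference 2 points; "with α (two-sided) = 2.5%, power= 90"%; 58 evaluable and 64 randomised per arm; yearly volumes 1000 micro and 500 macro, so the macro share is p = 500/1500 = 1/3.

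**Assumptions.** The trial's mix follows the yearly volumes. The SD of 3 covers both biopsy types together. The macro-minus-micro gap in mean D4 pain is g = 0 to 2 points. The documents give none of these.

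**1. The plan's own figure.** The plan says "it is necessary to include 58 patients per group (174 patients in total". With two-sided alpha 0.025, difference 2 and SD 3, the exact noncentral-t calculation first reaches 90% at 58 per arm (power 90.5%). The normal approximation gives 56. The stated figure is reproduced.

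**2. Chance imbalance in the macro share between two arms.** SD of the difference = √(2 × p(1 − p)/n).

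| n per arm | SD | 95% range (1.96 × SD) | Chance of 10 points or more, one comparison | Same, at least one of the two comparisons with control |
|---|---|---|---|---|
| 64 | √(2 × 0.2222/64) = 0.083 | ±16 points | 22% | 37% |
| 58 | √(2 × 0.2222/58) = 0.088 | ±17 points | 28% | 45% |

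The one-comparison chances are exact binomial results. The last column is from 1,000,000 simulated trials.

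**3. What that does to the pain difference.** The shift is g times the imbalance. At 58 per arm its 95% range is ±0.17 points for g = 1 and ±0.34 for g = 2. The standard error of the difference in means is 3 × √(2/58) = 0.557. For g = 2 the shift has SD 2 × 0.0875 = 0.175, and the rest of the standard error is √(0.557² − 0.175²) = 0.529. The shift is thus a component of the 0.557, not an addition to it.

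**4. Type I error of the unadjusted, unstratified t-test.** With 50,000 simulated trials per setting and nominal level 0.025, the result is 0.0250 for g = 1 and 0.0261 for g = 2. It is also 0.0253 for g = 3, beyond the range used here. The test keeps its level.

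**5. Gain from accounting for type.** Variance explained = g² × p(1 − p)/9. Residual SD = √(9 − g² × 2/9). Power is noncentral t at 58 per arm.

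| g (assumed) | Variance explained | Residual SD | Power |
|---|---|---|---|
| 0 | 0% | 3.000 | 90.5% |
| 1 | 2.5% | 2.963 | 91.2% |
| 2 | 9.9% | 2.848 | 93.3% |

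**6. Stratifying without adjusting.** If the blocks are stratified but the t-test ignores the stratum, the simulated type I error falls to 0.023 for g = 1 and 0.017 for g = 2. The test becomes conservative, because its standard error still contains variation that the design has removed.

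**The case against.** The strongest case against raising this is that nothing in the plan fails. The randomised comparison is unbiased, the test holds its level, and the sample size is reproduced. No part of the documents says that micro and macro biopsies differ in D4 pain, esthetic impact or bleeding, and the 2:1 split is the department's yearly workload rather than the expected trial mix. If the gap is small the gain is close to nothing, and the trial meets its 90% power target either way. All of this stands. It makes the point optional and conditional.

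Three stronger readings are tempting, and the documents support none of them.

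- *A reader might infer that the missing factor biases the result or inflates false positives.* Chance imbalance is not systematic, and step 4 shows the type I error intact.
- *A reader might set a shift of up to 0.34 points beside the 2-point target as a further error.* If the 25-patient pilot included both types (not stated), the SD of 3 already contains it, and counting it again would be double counting.
- *A reader might conclude that the trial is definitely unstratified.* The synopsis describes allocation in one parenthesis. It names no factor, and a fuller randomisation section could. The sponsor can settle this in one line.

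It can also be said that stratified allocation is the wrong place to act, since prespecified adjustment recovers most of the gain without it. That is right, and the fix is ordered accordingly. A pain score is also taken at D0 and could serve as a further covariate, but the documents give no correlation from which to size its value.

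**Conclusion.** The point holds as a minor, low-cost improvement. The synopsis leaves unused a baseline factor that is known at allocation and plausibly related to the primary endpoint. Over an assumed gap of 0 to 2 points, using it would take power at 58 per arm from 90.5% to at most about 93.3%, with no gain if the two types hurt equally. The planned comparison is valid without the change and the total of 192 patients need not move. The size rests on the three assumptions listed with the inputs: the trial's mix, the coverage of the SD, and the pain gap. No size can be given for esthetic impact or bleeding, because the documents offer no figures for them.

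**What to change.** 1. Record biopsy type (micro or macro) at randomisation. The synopsis does not say whether the registration form is completed after the biopsy, so the field should sit wherever the procedure performed is certain to be known.
2. In the SAP, prespecify the D4 pain comparison as a linear model with arm and biopsy type, in place of the plain Student test. This does not touch the allocation and can be done while the SAP is still to be written.
3. If allocation can still be changed, also stratify the blocks by micro/macro. The analysis must then include the stratum, for the reason in step 6.
4. State in the randomisation description whether any stratification factor is used.

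The cost is one data field and one model term. With stratification, add two block lists instead of one and one more incomplete block. With a single centre and two strata, over-stratification is not a concern.

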[figure not shown]

SYNOPSIS (English)	
Title	Pain monitoring after breast biopsy: benefit of e-health
Acronym	BIO-PSY
Pathology	Breast cancer
Protocol codes	Sponsor Code : PRO ICM 2020-06 BIO ID-RCB: 2020-A00836-33 N° NCT : NCT04456920
Study Sponsor	Institut régional du Cancer de Montpellier - ICM Clinical Research and Innovation Department (DRCI) [name] – France Contact Name : Mme [name] Mail : [contact] [contact] [contact]
Clinical trial coordinators	[name] [name] ICM Department of Radiology [contact] E-mail : [contact] Clinical trial co-coordinator : [name] [name], Ph.D ICM Department of Supportive Care [contact] E-mail : [contact]
Methodology and data management Center	Institut régional du Cancer de Montpellier - ICM Biometrics Unit Contact : Mme [name] [contact] E-mail : [contact]
Project manager	Institut régional du Cancer de Montpellier - ICM DRCI - Promotion Unit Contacts : [name] [name] [contact] E-mail : [contact]
Study design	Monocentric, prospective, open-labeled, randomized controlled trial
Trial sites	1 participating center
Number of planned patients	Expected number of patients : 192

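### The order of D0 scoring and allocation is not fixed in an open-label trial, so the only baseline pain, anxiety and esthetic scores may be given after the patient learns her arm

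*Combined protocol and SAP*

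**What the plan says.** All references are to the synopsis in the combined protocol and SAP.

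- **Study design:** "Monocentric, prospective, open-labeled, randomized controlled trial".
- **Treatment modalities, assignment:** "After breast biopsy and randomization (random bloc method and ratio 1:1:1), patients will either be in the" one of three groups: phone consultation, application on a connected device, or standard care.
- **Treatment modalities, D0 entry:** "D0 = Randomization + Evaluations of pain, anxiety and esthetical impact (with numeric scale". The experimental contacts start at D1.
- **Study endpoints, secondary:** the pain entry reads "Pain score assessed using a numeric pain scale administered after to biopsy and during the consultation of results announcement (approximately D10". The entry for anxiety follows the same pattern and adds D4: "Anxiety score assessed using a numeric anxiety scale administered after to biopsy, at 4 days (D4". So does the entry for esthetic impact: "Esthetic impact score assessed using a numeric esthetic scale administered after to biopsy, at 4 days (D4". Each places the first score relative to the biopsy only.
- **Study endpoints, insomnia:** "Insomnia score assessed using the Index of Severity of Insomnia administered during the baseline visit". This is the only measure tied to a named baseline visit.
- **Statistical considerations:** the primary endpoint, D4 pain, is compared between each experimental arm and control. Secondary endpoints are compared between each experimental arm and control, and between the two experimental arms. The tests named for continuous variables are Student and Wilcoxon / Kruskal-Wallis. No covariate model or change score is described. The SAP is to be written before the database is closed.

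**The concern.** A baseline score is useful because allocation cannot have influenced it. Here the patient will learn, on the day of the biopsy, whether she gets daily calls, an application or nothing extra. If she rates pain, anxiety and appearance after hearing this, the rating can include relief or disappointment about the arm. Anxiety is the most plausible carrier. The trial's own rationale (Background and Rationale; Benefit) is that communication with staff lowers anxiety and that anxiety is related to pain.

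The sponsor already applies the principle elsewhere. For a D10 consultation held by telephone, Treatment modalities insists that the scores be collected before the biopsy result is given. There is no equivalent rule at D0.

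Three things are at stake:

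- the between-arm comparison of D0 scores, which the endpoint list and the general sentence on secondary endpoints together imply;
- the check that the arms were alike at the start;
- any D4 or D10 analysis that adjusts for D0 or subtracts it.

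Even with a clean order, testing D0 scores as outcomes has little meaning: with no intervention delivered, any difference is chance.

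**Working it through.** **1. The order in the text.** The assignment sentence puts randomization after the biopsy. The endpoints put the first scores after the biopsy. The D0 entry joins randomization and scoring with a plus sign. Scoring then allocation, and allocation then scoring, both satisfy all three statements. No statement says when the patient is told her arm.

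**2. The plan's own figure.** Inputs from Statistical considerations: difference 2, SD 3, two-sided alpha 2.5%, power 90%. The two-sample t-test gives 57.13, rounded up to 58 per group, as stated; power at 58 is 90.5%. Then 174 × 1.10 = 191.4, rounded up to 192, as stated. D0 plays no part in this calculation.

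**3. Effect of a D0 shift.** Let s be the shift in mean D0 score (experimental minus control) caused by knowing the arm, and r the within-arm D0–D4 correlation. Assume SD 3 at both times and that the reaction does not itself change the D4 score. The bias in the D4 difference is then:

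- unadjusted D4 comparison (as planned): 0
- change from D0: −s, that is 0.5 to 1 point in size
- baseline-adjusted (ANCOVA): −r × s

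The values of s (0.5 and 1 point) and r (0.3 to 0.7) are assumptions; the documents give neither.

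**4. Direct D0 comparison.** Standard error = 3 × √(2/58) = 0.557. A shift of 0.5 gives 0.5/0.557 = 0.90 standard errors, and 1 point gives 1.80. With the noncentral t distribution (114 df, two-sided 2.5%), the chance of a significant result is 8.9% and 32.1%, against 2.5% with no shift.

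**5. Adjusted D4 comparison, should the SAP adopt one.** Residual SD = 3 × √(1 − r²). The noncentrality is r|s| / (residual SD × √(2/58)) for false positives, and (2 − r|s|) / (residual SD × √(2/58)) for power when the shift masks a true 2-point benefit.

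| r | Residual SD | Power, no shift | Shift | Bias (size) | False positives | Power if masked |
|---|---|---|---|---|---|---|
| 0.3 | 2.86 | 93.1% | 0.5 | 0.15 | 3.1% | 88.5% |
| 0.3 | 2.86 | 93.1% | 1.0 | 0.30 | 4.9% | 82.2% |
| 0.5 | 2.60 | 96.8% | 0.5 | 0.25 | 4.5% | 91.1% |
| 0.5 | 2.60 | 96.8% | 1.0 | 0.50 | 11.2% | 79.8% |
| 0.7 | 2.14 | 99.7% | 0.5 | 0.35 | 8.6% | 96.9% |
| 0.7 | 2.14 | 99.7% | 1.0 | 0.70 | 30.8% | 83.9% |

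The false-positive column is two-sided. The no-shift power column shows what a clean baseline would be worth: about 93% to 99.7%, against 90.5% unadjusted.

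**The case against.** **The plus sign lists what happens at a visit; it does not set a sequence.** This stands. A reader might infer from the entry that randomization comes first and that patients are scored knowing their arm. The documents do not say so. They also do not exclude it. The text is a synopsis, and a fuller schedule might settle the matter, but none is in the documents.

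**The primary analysis does not use D0.** This also stands. A reader might take the power and false-positive figures as a threat to the primary result. They are not: the plan compares D4 scores without adjustment, and the bias there is zero. The adjusted analysis in step 5 is not in the plan.

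**The direction is uncertain.** Relief in the experimental arms, or disappointment in control, would lower experimental D0 scores relative to control. Adjustment would then understate a benefit. A false positive in favour of the intervention needs the opposite shift, for which the documents suggest no mechanism. At a 0.5-point shift with r = 0.5, power is still 91.1%, no worse than the planned 90%. The calculation also uses the pain SD; the documents give none for anxiety, the score most exposed.

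**No objective names D0.** The objectives for pain, anxiety and esthetic impact concern D4 and about D10. That makes the D0 comparison marginal, but the endpoint list includes the post-biopsy scores and the analysis text compares secondary endpoints between arms, so as written it would be run.

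What survives is a gap in the procedure. It matters because the covariate decision is still open, and because a score given after disclosure cannot be repaired later.

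**Conclusion.** The concern holds as an unspecified order that permits bias, not as proof that bias occurs. The open-label design, the missing sequence and the lack of any other baseline for these three scores all come from the documents. The consequence is moderate: nothing for the planned primary comparison, and real exposure for the D0 comparison, the baseline check and any later adjusted or change-score analysis. The 9% to 32% and the 0.15 to 0.70 points illustrate that exposure under the assumed shifts and correlations; they are not estimates for this trial. The correction is worth making because it is cheap and turns a score already collected into a usable covariate.

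**What to change.** 1. State one D0 sequence: biopsy, D0 scales completed and recorded, then allocation, then disclosure of the arm.
2. Label the D0 pain, anxiety and esthetic scores as baseline, describe them by arm, and remove them from the outcomes compared between arms.
3. With that order secured, specify in the SAP that the matching D0 score is a covariate for the D4 and D10 scores. This changes the planned unadjusted comparison, so it should be fixed before the data are examined.
4. For any patient already scored after disclosure, record this, and do not use that D0 score as a covariate or in a change score.

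The cost is a change of order within one visit and a few lines of text. No assessment is added, and 58 per group and 192 in total stay as they are. The documents do not describe the D0 workflow, so the site should confirm that the order is practicable.

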	
At D1, D2 and D3, patients in the experimental group 1 will receive a call from a neuro-psychologist during which pain, anxiety and esthetical biopsy impact will be assessed using numeric or visual analog scales during a semi-direct interview. During this call, any adverse events related to the breast biopsy will also be noted, as well as the amount, nature and dose of analgesics, anxiolytics, anti-depressants, anti-inflammatory and hypnotics taken linked to the biopsy. If detected, pain or significative distress would be specifically managed.
 
Patients in the experimental group 2 will be asked by SMS or notification to connect to the application in order to complete online the numeric and visual analog scales of pain, anxiety and esthetical impact. Any adverse events related to the breast biopsy will also be noted online, as well as the amount, nature and dose of analgesics, anxiolytics, anti-depressants, anti-inflammatory and hypnotics taken for the biopsy. If detected, pain or significative distress would be specifically managed.
 
At D4 post biopsy, all patients (of the 3 groups) will receive a phone call from a neuro-psychologist to assess pain, anxiety and esthetical impact, using numeric scales, and to collect adverse events. If detected, pain or significative distress would be specifically managed.
 
And at D10 (+/- 3 days), all patients will have the consultation of biopsy results announcement. This visit will be held either on-site or by videoconference. At the beginning of this consultation, pain, anxiety and esthetical impact will be assessed using numeric scales. The adverse events related to the breast biopsy will be collected as well as the amount, nature and dose of analgesics, anxiolytics, anti-depressants, anti-inflammatory and hypnotics taken for the biopsy and its findings. Insomnia will be evaluated by the Insomnia Severity Index. If detected, pain or significative distress would be managed as usually in the center. If the consultation is to be done by telephone, it is essential that this data collection be done before the results are announced.

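### The D4 primary pain score is taken by the same professional role that makes the Group 1 calls, with no stated masking or score-first rule, so reported pain in the phone arm could shift in either direction.

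*Combined protocol and SAP*

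**What the plan says.** The Study design row of the synopsis reads "Monocentric, prospective, open-labeled, randomized controlled trial". Under Study endpoints, the primary endpoint is a numeric pain score collected by telephone on D4.

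Treatment modalities describes the contacts before D4:

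- **Group 1 (phone).** The plan states that "patients in the experimental group 1 will receive a call from a neuro-psychologist" on each of the three days before D4. Each call is a semi-directed interview in which the patient's pain is scored.
- **Group 2 (connected objects).** "Patients in the experimental group 2 will be asked by SMS or notification to connect to the application". No neuro-psychologist call is scheduled.
- **Group 3 (control).** Standard care, with no scheduled contact before D4.

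On D4, "all patients (of the 3 groups) will receive a phone call from a neuro-psychologist to assess pain" along with anxiety and esthetic impact. The same call collects adverse events, and pain or distress that is detected is to be managed. The order of scoring and management within the call is not given.

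For D10, the same section places scoring at the start of the results consultation. If that consultation is by telephone, the data must be collected before the result is given.

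Statistical considerations names two primary comparisons, telemedicine versus control and smartphone versus control. It gives 58 patients per group, SD 3, a 2-point difference, two-sided alpha of 2.5% and 90% power.

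**The concern.** Patients in this trial cannot be blinded, and that limitation applies to all arms. The overlap of intervention and measurement does not. In Group 1 they share the professional role, the telephone and the type of scale, so the D4 call resembles a fourth intervention call. For the other two groups it is the first scheduled call from that role.

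A patient may answer differently to someone she has spoken to three times, and a caller who knows the arm may put the question differently. Either would move the reported score in one arm without moving the pain itself. It would enter telemedicine versus control, a primary comparison, and the secondary comparison of telemedicine with smartphone. Smartphone versus control would be largely spared. No planned analysis in the available text could separate such a shift from a real effect.

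The D10 rule shows that the plan already recognises that the order of events in a contact can affect a score. The primary endpoint has no matching rule.

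**Working it through.** **1. The overlap.** Contacts set side by side, from Treatment modalities:

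| | Scheduled neuro-psychologist calls D1-D3 | D4 score taken by | Rule that the score comes first |
|---|---|---|---|
| Group 1 | 3 | neuro-psychologist, by phone | none stated |
| Group 2 | 0 | neuro-psychologist, by phone | none stated |
| Group 3 | 0 | neuro-psychologist, by phone | none stated |
| All groups, D10 | – | role not named | start of consultation |

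Group 2 patients may receive unscheduled calls after an alert, because Study endpoints counts alerts that lead to a call. The text does not say who makes them.

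**2. The plan's own figure.** Inputs from Statistical considerations: difference 2, SD 3, two-sided alpha 0.025, power 0.90.

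- Normal approximation: n = 2 × [3 × (2.241 + 1.282) / 2]² = 55.85, so 56 per group.
- Noncentral t: 58 per group, with power 90.5%. This matches the plan.
- Total: 3 × 58 = 174, and 174 × 1.10 = 191.4, rounded to 192.

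The sample size reproduces and this point does not affect it.

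**3. Effect of a reporting shift towards less reported pain in Group 1.** The shift is an assumption; the documents give no value.

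- Standard error: SE = 3 × √(2/58) = 0.557.
- Smallest significant observed difference: t(0.9875; 114 df) × SE = 2.271 × 0.557 = 1.27 points. It is 1.20 points at 64 per group.
- With no true effect, the noncentrality is shift / 0.557. The chance of a significant result favouring the phone arm is the upper tail of the noncentral t beyond 2.271.

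| Assumed shift (points) | Noncentrality | False phone-arm benefit, n = 58 | Same, n = 64 | Any significant result, both tails, n = 58 |
|---|---|---|---|---|
| 0 | 0 | 1.25% | 1.25% | 2.5% |
| 0.25 | 0.449 | 3.6% | 3.8% | 4.0% |
| 0.5 | 0.898 | 8.8% | 9.5% | 8.9% |
| 0.75 | 1.346 | 18% | 20% | 18% |
| 1.0 | 1.795 | 32% | 35% | 32% |

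**4. A shift in the other direction.** If familiarity leads Group 1 patients to disclose more pain, a true 2-point benefit is measured as less. At 58 per group, power falls from 90.5% to 66% with a 0.5-point shift (apparent difference 1.5) and to 32% with a 1.0-point shift (apparent difference 1.0).

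**The case against.** **The plan has a safeguard.** D4 uses one mode, one professional role and numeric scales in all three arms. This avoids a difference in collection mode, notably for the app arm. It stands, but it does not equalise prior contact. The D10 score is a further partial check, since the text does not assign it to the neuro-psychologist, but it is a different time point and not the primary endpoint.

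**Only a synopsis is available.** Scripts, rotas and question order are often set out elsewhere, and the SAP is still to be written. This stands. The point is that the available text does not describe these protections. If another document does, a cross-reference settles the matter.

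**Masking the caller does not blind the patient.** Courtesy arises in a patient who knows her arm, and a masked call sheet achieves little if the caller made the earlier calls. This stands and limits what any fix can do.

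**Hiding history could affect care.** The D4 call also collects adverse events and leads to management of detected pain or distress. This stands, so any masking must end once the score is recorded.

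**Modest shifts rarely reach the target difference.** With SE 0.557, an observed difference of at least 2 points needs (2 − 0.5)/0.557 = 2.69 standard errors under a 0.5-point shift, a chance of roughly 0.4%. Under a 1.0-point shift it needs 1.80 standard errors, roughly 4%. This is correct, but the test is significant from 1.27 points.

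A reader might infer that one person delivers the intervention and scores its result, that this person also manages the pain, or that controls speak to a stranger. The documents support none of these. They name a role, do not say who manages detected pain, and place a D0 evaluation in every arm without naming the staff.

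**Conclusion.** The point holds at the level of role. An arm-specific measurement bias in one of the two primary comparisons is possible, and the available text describes nothing to limit it.

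The size is unknown. The illustration of 3.6% to 32% false phone-arm benefit, against 1.25% with no shift, rests on assumed shifts of 0.25 to 1.0 points, no true effect, SD 3, 58 per arm and a two-sided 2.5% t test.

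A reader might take these figures to show that the bias favours the phone arm. They do not: the documents give no direction, and familiarity could equally raise reported pain and hide a benefit. Nor do they make the trial invalid. This is a cheap improvement that should be made, with moderate confidence that it matters in practice.

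**What to change.** Add to the D4 procedure, using existing staff:

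1. Ask the numeric pain scale first, word for word from one script in all three arms, and lock the score before any other discussion.
2. Do not show the caller the arm or the D1-D3 answers until the score is locked. After that they are available for adverse event collection and care, which this change leaves as they are.
3. Where more than one neuro-psychologist makes calls, the D4 caller is not the one who made that patient's D1-D3 calls. The documents give no staffing number. If there is only one caller, item 1 still applies, and the report should state the overlap.
4. Record caller identity. If callers overlap in Group 1, describe D4 scores by same versus different caller within Group 1 only. Across arms, scheduled prior contact coincides with allocation, so an analysis by prior contact could not separate the two. Full compliance with item 3 leaves nothing to compare, which is acceptable.

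The cost is a short script, a two-stage call sheet, a rota rule and one data field, with no added patients or visits. Scheduling becomes slightly less flexible. Some patients will reveal their arm, and because all of them know it, the bias is reduced but not removed.
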